10.1.2 Secondary Endpoints

Data from a preliminary study conducted at UMass ([name], unpublished data) in which FMD was measured in patients after non-STEMI ACS was used for primary endpoint power calculations. In that pilot study, mean FMD was $9.6 \pm 2.0\%$ in normal controls (n=16) and $4.6 \pm 2.8\%$ in ACS patients (n=22). Based on these data, a sample size of 48 total subjects (24 each randomized to ifetroban or placebo) is required to detect a 50% increase in FMD with 80% power for an analysis of covariance of each treatment separately with a two-sided alpha=0.05. Data from the RIGOR study was used to determine the power to detect a difference in non-platelet TXA₂ generation with drug treatment.³ With a median 11-dhTXB₂ of 330 pg/mg creatinine, a 33% reduction would be to 220 pg/mg creatinine (reduction from 5.8 to 5.4 in the natural log scale) with a s.d. of 0.55 in the log scale. A sample size of 48 total subjects (24 each randomized to ifetroban or placebo) will have the ability to detect treatment group differences described above with 80% power for an analysis of covariance of each treatment separately with a two-sided alpha=0.05, assuming an $R^2 = 0.50$ with the baseline level and treatment included in the model.

10.2 Statistical Analysis Plan

Descriptive statistics of patient characteristics will be generated using conventional methods. The main analysis of the outcome data will be a standard ANCOVA approach (SAS PROC GLM). The full model will be fit for change in RHI (or other measure of interest) as the outcome for patient i based on treatment group (as two dummy (0,1) variables: x_1, x_2), a vector of patient characteristics $x_{3,i}$, and an error term e_i : $\ln(11-dhTXB_2)_i = b_0 + b_1x_{1i} + b_2x_{2i} + b_3x_{3i} + e_i$. We will test the main effects (treatment as well as patient characteristics) included in the model with the treatment main effects always included. We will investigate interactions between patient characteristics and treatments to provide insight into the effect of these treatments on the outcomes overall and the effect in larger patient subgroups.

11 Data Management

Study data will be recorded in a Research Electronic Data Capture (REDCap) database in the secure regulated environment at the UMass Medical School. REDCap is a secure, web-based application designed to support data capture for research studies, providing 1) formatted data entry screens; 2) audit trails; 3) automated export procedures for seamless data downloads to statistical packages; 4) procedures for importing data from external sources; and 5) an Application Programming Interface that enables it to communicate with our web-based randomization system. Data will be exported from REDCap into SAS (SAS Institute) for all analysis.

12 Regulatory Issues

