8.1 Primary Endpoint

The primary trial endpoint will be change from baseline in on-treatment Reactive Hyperemia Index (RHI) measured by peripheral arterial tonometry (PAT) using the standard protocol described in Appendix C .

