8.2 Secondary Endpoints

Secondary trial endpoints will be the change from baseline in on-treatment:

- Brachial % flow-mediated vasodilation (FMD) using the standard protocol described in Appendix B.

- Urine 11-dhTXB₂ as measured by mass spectrometry or immunoassay and normalized to urine creatinine.

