10.1 Sample Size Calculations

10.1.1 Primary Endpoint

Data from several studies was used to determine the power to detect a difference in RHI with drug treatment. In one study of PAT reproducibility in cardiovascular patients, the intra-patient standard deviation was 0.31.⁵⁵ In a meta-analysis of >1500 subjects with cardiovascular disease the mean RHI was 1.52.⁵⁶ Based on these data, a sample size of 48 total subjects (24 randomized each to ifetroban or placebo) is required to detect a 20% increase in RHI with over 85% power with a two-sided alpha of =0.05. Adjusting for 10% loss to follow up, we will need 52 randomized subjects.

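### The only model equation in section 10.2 has the level of ln(11-dhTXB2) as its outcome, not change in RHI, and the Visit 1 value is not named as a retained term

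*Combined protocol and SAP*

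**What the plan says.** Section 10.2 calls the main analysis a standard ANCOVA in SAS PROC GLM. Its outcome is given in words: "The full model will be fit for change in RHI (or other measure of interest) as the outcome for patient". The only equation in the section then reads "\ln(11-dhTXB_2)_i = b_0 + b_1x_{1i} + b_2x_{2i} + b_3x_{3i} + e_i". Its right side has an intercept, two treatment dummies, an unlisted vector of patient characteristics and an error term. Main effects are to be tested "with the treatment main effects always included". No other term is guaranteed, and neither 10.2 nor the Statistical Methods entry of the protocol summary names the baseline value.

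The endpoints are stated elsewhere. Section 8.1 says "The primary trial endpoint will be change from baseline in on-treatment Reactive Hyperemia Index (RHI". Section 8.2 says "Secondary trial endpoints will be the change from baseline in on-treatment", and lists FMD and urine 11-dhTXB2.

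Section 10.1.2 bases the 11-dhTXB2 power on R² = 0.50 "with the baseline level and treatment included in the model". Its effect and spread are a "reduction from 5.8 to 5.4 in the natural log scale) with a s.d. of 0.55 in the log scale". Section 10.1.1 gives no baseline term or R² for RHI, only that "the intra-patient standard deviation was 0.31".

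**The concern.** The equation disagrees with its own sentence in two ways: it shows a secondary measure where the prose names RHI, and a level where the prose names a change. It also disagrees with section 8.2, which defines 11-dhTXB2 as a change.

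The level-or-change difference would be harmless if the Visit 1 value were always in the model. Writing Y3 − Y1 = b0 + b1·T + b2·Y1 + e and moving Y1 to the right gives Y3 = b0 + b1·T + (b2 + 1)·Y1 + e, so b1 is the same either way. Without that term the two analyses give different estimates, standard errors and p-values. Section 10.2 does not require the term, so two analysts could both follow it and report different primary results. Precision that a measurement already taken would supply could also be lost.

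**Working it through.** **11-dhTXB2: inputs (10.1.2).** δ = 5.8 − 5.4 = 0.4; SD 0.55; R² = 0.50; 24 per arm; two-sided α = 0.05; stated power 80%.

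**Formula.** Noncentral t with noncentrality δ / (σ·√(2/24)), 46 df without baseline and 45 with it.

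**The plan's own figure.** With residual SD 0.55·√0.50 = 0.389, power is 93.6% (94.6% by the normal approximation), and 15 per arm would give 80% by the normal approximation. The stated 80% at 24 per arm is therefore not reproduced. It may be a floor, because the FMD inputs (difference 0.5 × 4.6 = 2.3, SD 2.8) do lead to 24 per arm. That is a separate matter.

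**Three readings of 0.55 and R².**
- A: 0.55 is the within-arm SD and R² covers baseline plus treatment. Residual variance = 0.5·(0.55² + 0.4²/4) = 0.171, SD 0.414. Implied Visit 1 to Visit 3 correlation r = √(1 − 0.171/0.3025) = 0.66.
- B: 0.55 is the total SD. Within-arm SD = √(0.3025 − 0.04) = 0.512; residual SD 0.389; r = 0.65.
- C: 0.55 is the within-arm SD and R² comes from baseline alone. Residual SD 0.389; r = 0.71.

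If the SD is equal at both visits (an assumption), the SD of change is the within-arm SD × √(2(1 − r)) = 0.454, 0.428 and 0.421.

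| Reading | Level, no baseline (as printed) | Change, no baseline | Baseline-adjusted |
|---|---|---|---|
| A | 69.4% | 84.7% | 90.0% |
| B | 75.4% | 88.7% | 93.1% |
| C | 69.4% | 89.7% | 93.1% |

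The last column is averaged over chance baseline imbalance (variance factor 1 + F(1,46)/46). Without that averaging it is 90.6%, 93.6% and 93.6%. The averaged gain over unadjusted change is 5.2, 4.5 and 3.5 points, so about 4 to 5.

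**RHI: inputs (10.1.1).** δ = 0.2 × 1.52 = 0.304; 24 per arm. The SD of change is 0.31·√2 = 0.438 if 0.31 is the within-patient SD, or 0.31 if it is already the SD of change. The adjusted residual SD is the SD of change × √((1 + r)/2). The correlation r is not in the documents and is assumed.

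| Meaning of 0.31 | No baseline | r = 0.3 | r = 0.5 | r = 0.7 | r = 0.9 |
|---|---|---|---|---|---|
| Within-patient SD | 65.2% | 82.2% | 76.6% | 71.3% | 66.5% |
| SD of change | 91.4% | 98.3% | 96.7% | 94.6% | 92.1% |

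The gain is 1 to 17 points in the first row and 1 to 7 in the second. In the first row power stays below the stated level of over 85% even with baseline. In the second it is above that level even without.

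**The case against.** The strongest reply is that this is incomplete wording and not a plan to leave baseline out. ANCOVA ordinarily means adjustment for the baseline value, the vector of patient characteristics can contain it, and 10.1.2 describes exactly such a model. The prose allows for other measures of interest, so the equation may be an example left uncorrected. Much of this stands. The joint reading leans towards adjustment, and the losses above arise only if the Visit 1 value is never entered. But none of these phrases names the term or keeps it in the model, and if the equation is only an example, the primary endpoint has no equation at all.

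The second reply is about size. A reader might infer that the baseline term decides whether 11-dhTXB2 reaches its stated 80%. On the plan's inputs it does not: on the endpoint as 8.2 defines it, unadjusted change already gives about 85% to 90%. Only the printed level equation falls short.

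A reader might also infer that covariates will be chosen on their p-values. Section 10.2 states no selection rule. Even if Visit 1 RHI were entered and dropped only when p ≥ 0.05, simulation (40,000 trials per setting) puts power within about 0.3 points of always keeping it, with type I error of 5.0% to 5.5%.

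**Conclusion.** The mismatch in the text is certain. The one equation in 10.2 contradicts its own sentence and sections 8.1 and 8.2, and it does not secure the baseline term that 10.1.2 assumes for the same outcome. This should be corrected, but its consequences are limited.

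- For 11-dhTXB2, the equation followed literally gives about 69% to 75% power, below the stated 80%. On the change endpoint the baseline term adds about 4 to 5 points, to about 90% to 94%. This rests on R² = 0.50 and on equal SDs at the two visits. At an assumed correlation of 0.5, which the plan does not state, the figures would be about 69% for unadjusted change and 81% adjusted.
- For RHI the gain is 1 to 17 points, or 1 to 7 under the other reading of 0.31. It depends on an assumed correlation and does not by itself settle whether power exceeds 85%.

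Two stronger conclusions are not supported. The primary endpoint is not in doubt: 8.1, the protocol summary and the prose of 10.2 all name change in RHI. Nor would the treatment comparison be biased: under randomisation, leaving baseline out costs precision only. What remains open is which model produces the primary estimate and p-value.

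**What to change.** Replace the equation in 10.2 with:

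change in RHI = b0 + b1·(ifetroban indicator) + b2·(Visit 1 RHI) + e

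State that Visit 1 RHI is always retained and that b1 is the primary estimate and test. One indicator is enough for two arms. Use the same form for FMD, and for 11-dhTXB2 on the log scale with ln(Visit 1 value) as covariate.

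The cost is one degree of freedom and a wording amendment made before unblinding, with IRB approval under 9.1 and 12.2 if the change is not administrative. No visit or sample is added: vascular testing and urine collection already take place at Visit 1. Appendix A does not list 11-dhTXB2 by name among the Visit 1 assays, but 8.2 already needs a baseline value for it.

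Listing any further covariates in advance and labelling the treatment interactions exploratory would be useful clarifications. They are optional and not part of this finding.

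### Section 10.2 does not fix the model behind the primary p-value, and its wording permits outcome-based covariate selection that can raise the two-sided type I error above 0.05

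*Combined protocol and SAP*

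**What the plan says.** Section 10.2 is the only analysis text for the primary endpoint. It names a standard ANCOVA in SAS PROC GLM and starts from a full model for change in RHI, with treatment terms and a vector of patient characteristics that is neither listed nor counted. It continues: "We will test the main effects (treatment as well as patient characteristics) included in the model with the treatment main effects always included". The next sentence begins: "We will investigate interactions between patient characteristics and treatments to provide insight".

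Section 10.1.1 sets the error rate and size for the primary endpoint: "a sample size of 48 total subjects (24 randomized each to ifetroban or placebo"), with "over 85% power with a two-sided alpha of =0.05".

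The Protocol Summary says only that continuous data are compared by ANCOVA. A model with the baseline level and treatment appears once, in section 10.1.2, as an assumption for the power of the secondary endpoint 11-dhTXB2. No section names baseline RHI as a covariate, and none says which fitted model supplies the primary p-value and interval.

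**The concern.** A clause that guarantees treatment a place has most to do if other terms can lose theirs, and a full model suggests a reduced one. On that reading, characteristics are tested against the outcome, some are dropped, and treatment is judged from what remains.

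The usual ANCOVA p-value assumes that the model was chosen without looking at the outcome. Covariates kept because they tested well have, in part, fitted the noise of this sample. The residual variance is then too small, the standard error of the treatment effect is too small, and the confidence interval is too narrow. With about 48 evaluable subjects this is not negligible unless candidates are few. At stake is whether the single primary test has the 0.05 level that section 10.1.1 gives it.

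**Working it through.** **1. The plan's own figure.** Inputs from section 10.1.1: "the mean RHI was 1.52", "the intra-patient standard deviation was 0.31", a 20% increase, 24 per arm, two-sided alpha 0.05.

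- Difference: 0.20 × 1.52 = 0.304.
- Standard error: 0.31 × √(2/24) = 0.0895.
- Ratio: 0.304 / 0.0895 = 3.40.
- Power (normal): Φ(3.40 − 1.96) = 92.5%. Noncentral t with 46 df: 91.4%.

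The claim of over 85% therefore holds as a lower bound when 0.31 is taken as the SD of the compared outcome. The calculation is a plain two-group comparison at 0.05 and makes no allowance for covariate selection, so 0.05 is the benchmark.

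**2. What the documents do not give.** The number of candidates, the retention threshold, the selection method and the variance the characteristics explain. All four are assumed below, over a range.

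**3. Simulation under no drug effect.** 48 subjects, 24 per arm, treatment always kept, backward elimination of the characteristics by p-value, treatment tested at two-sided 0.05 in the final model.

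- Design A: baseline outcome (r = 0.6) always kept; thresholds 0.05 and 0.10; candidates explain 0% or 20% of variance; 10,000 trials per case; Monte Carlo SE √(0.05 × 0.95 / 10,000) = 0.0022.
- Design B: no forced baseline; independent normal covariates; thresholds 0.05, 0.10 and 0.20; explained variance 0% or 30%; 20,000 trials per case; Monte Carlo SE √(0.05 × 0.95 / 20,000) = 0.0015.

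| Procedure | Design A | Design B |
|---|---|---|
| Model fixed in advance | 0.048-0.054 | 0.045-0.053 |
| Elimination, 4 candidates | 0.056-0.071 | 0.052-0.060 |
| Elimination, 8 candidates | 0.062-0.083 | 0.059-0.075 |
| Elimination, 15 candidates | 0.074-0.111 | 0.074-0.105 |
| Elimination, 20 candidates | not run | 0.091-0.134 |

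A further run under the same reading gave about 5.4-7.2%, 5.6-8.6% and 7.5-11% for 4, 8 and 15 candidates. Across all runs the rounded ranges are 5-7%, 6-9% and 7-11%. The lowest value for 4 candidates (0.052) is within simulation error of 0.05.

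**4. Sensitivity.**

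- One-at-a-time screening instead of backward elimination (design B): 0.052-0.058 with 4 candidates, 0.057-0.069 with 8, 0.066-0.079 with 15.
- All 57 subjects of the Protocol Summary and section 6.2 analysed, backward elimination: 0.061-0.069 with 8 candidates (threshold 0.05); 0.094 with 15 (threshold 0.10, explained variance 30%).

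Neither a milder selection method nor the larger sample removes the excess.

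**5. Interactions.** Eight independent treatment-by-characteristic tests at 0.05 give 1 − 0.95^8 = 34% for at least one nominally significant result under no effect. Eight is again an assumption. This bears on subgroup statements, not on the primary test.

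**The case against.** The strongest reply is that section 10.2 states no selection rule. It says that the full model is fitted and that the effects in it are tested. Testing each coefficient inside one fitted model satisfies every word and leaves the level near 0.05, as the first row of the table shows. The guarantee for treatment can also be read as ordinary hierarchy: treatment stays in whenever its interactions are examined, which is the subject of the next sentence. The sizes come from assumed inputs. Eight matches the number of factors in Table 2, but those are risk factors for urine thromboxane, not for RHI, and nothing makes them the candidates here. Figures above 10% need 15 or more candidates. Finally, this is a small, single-center phase 2b trial, and interactions are looked at for insight only.

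Much of this stands. A reader might infer that the primary p-value does come from a data-selected model and that its type I error does exceed 0.05. The documents do not support that: they contain no elimination step, threshold, candidate count or reduced model. Nor do they say that covariates will be chosen after unblinding, because they are silent on timing. A reader might also infer that the interaction search damages the primary test. It does not.

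What the reply does not supply is the fixed model that its benign reading needs. That reading holds 0.05 only if the covariates are set in advance, and no list exists. The paragraph is also too loose to assume that one was intended: its text takes change in RHI as the outcome while its equation has the log of 11-dhTXB2 on the left, and it uses two treatment dummies for a two-arm trial.

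**Conclusion.** The concern holds in conditional form. Section 10.2 tests unlisted patient characteristics on the outcome data, protects only treatment, and does not say which fit is primary. Outcome-based selection is permitted and is the most natural reading, but it is not written as a rule.

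If characteristics are dropped on their tests, the primary two-sided level at 48 subjects is roughly 5-7% with 4 candidates, 6-9% with 8 and 7-11% with 15. The true size cannot be derived from the documents; it could be negligible with few candidates. If the model is fixed in advance, the level is about 5%. On either reading, nobody can confirm from the current text that 0.05 was held.

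**What to change.** Replace the testing sentence in section 10.2 with text to this effect:

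> The primary p-value and 95% confidence interval come from one ANCOVA fixed before unblinding: treatment plus the Visit 1 value of the endpoint. Further covariates enter this model only if they are listed here in advance. No covariate is added or removed on the basis of its test in the outcome data. Models with other patient characteristics, and all interaction models, are sensitivity or exploratory analyses and do not replace the primary result.

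Treatment plus baseline is the simplest choice. Any covariate set fixed in advance would also hold the level, provided that it is written down before unblinding.

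The cost is SAP wording. RHI at Visit 1 is already scheduled in section 4.3.1 and Appendix A, so no subjects, visits or measurements are added. The small downside is that a characteristic found afterwards to be prognostic cannot sharpen the primary estimate; it can still be shown in a sensitivity analysis.

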12.1 Ethics and Good Clinical Practice

This study will be carried out in compliance with the protocol. These procedures are designed to ensure adherence to Good Clinical Practice, as described in: 1) ICH Harmonized Tripartite Guidelines for Good Clinical Practice 1996, and; 2) US 21 Code of Federal Regulations dealing with clinical studies (including parts 50 and 56 concerning informed consent and IRB regulations). All investigators and study personnel agree to adhere to the instructions and procedures described in it and hereby to adhere to the principles of Good Clinical Practice to which it conforms.

12.2 Institutional Review Board

Before implementing this study, all required documents including the protocol, proposed informed consent form and Investigator's Brochure must be reviewed and approved by the UMMS IRB. Any amendments to the protocol, other than administrative ones, must be approved by this committee.

12.3 Informed Consent

The investigator or designee must explain to each participant the nature of the study, its purpose, the procedures involved, the expected duration, the potential risks and benefits involved and any discomfort it may entail. Each participant must be informed that participation in the study is voluntary and that he/she may withdraw from the study at any time and that withdrawal of consent will not affect his/her subsequent medical treatment or relationship with the treating physician.

The informed consent form(s) and any amendments must be submitted by the investigator for IRB approval.

Laboratory Studies					
UrineTXB ₂ -M	X				
Urine Prostanoids (8-iso-PGF _{2α} ; 6-ketoPGF _{1α} ; 2,3-dinor-6-ketoPGF _{1α})		X		X	
Urine Creatinine	X	X		X	
Plasma ICAM-1; APC; TF		X		X	
Serum creatinine; hs-CRP; NT pro-BNP		X		X	
^a Performed while still on study drug.					

15 Appendix B: Brachial Reactivity

15.1 Introduction

Healthy blood vessels dilate in response to an increase in blood flow, a phenomenon known as flow-mediated dilation (FMD).⁵⁷ FMD is predominantly a function of endothelial nitric oxide (NO) release that relaxes underlying vascular smooth muscle cells. Endothelial release of PGI₂ also plays a role in mediating FMD. TXA₂, in addition to being a potent platelet activator, is also a potent vasoconstrictor that antagonizes the effects of NO and PGI₂.

Vascular dysfunction is associated with the development and presence of atherosclerosis and characterized by an impaired vasodilatory response to blood flow. FMD is traditionally measured non-invasively by ultrasound in the brachial artery following a period of blood flow cessation caused by an inflated blood pressure cuff.⁵⁸ Typically, the cuff is inflated to at least 50 mm Hg above systolic pressure to occlude arterial inflow for 5 minutes. This causes ischemia and consequent dilation of downstream resistance vessels via autoregulatory mechanisms. Subsequent cuff deflation induces a brief high-flow state through the brachial artery (reactive hyperemia) to accommodate the dilated resistance vessels. The resulting increase in shear stress causes the brachial artery to dilate. The ratio of the brachial artery diameter after the occlusive period to that at baseline is recorded as the percent FMD. Impaired FMD is associated with cardiovascular risk factors and the development of clinical cardiovascular disease. The protocol that will be used is based on guidelines published by the American College of Cardiology.⁵⁹

15.2 Protocol

15.2.1 Subject preparation

1. Prior to the study, ensure the patient has fasted for at least 4 hours, and has refrained for at least 8 hours from caffeine, tobacco, vitamins or medications that might affect vascular tone. The patient may wish to use the restroom prior to the study.
2. The brachial reactivity study will be conducted in a quiet, dimly lit, temperature-controlled exam room to reduce fluctuations in vascular tone.
3. Cell phones or paging devices should be silenced, and restrictive clothing that could interfere with blood flow to the arms should be removed. The patient should also remove watches, rings, or other jewelry on the hands or fingers.
4. The patient should be supine and comfortable for 15 minutes so as to attain a cardiovascular steady-state. Place the two arm supporters along each of the patient's sides.
5. Place a blood pressure cuff on the arm to be occluded during the brachial reactivity study. Apply the cuff snugly, but without excess pressure. Do not inflate the cuff at this time.
6. The brachial artery is imaged above the antecubital fossa in the longitudinal plane (Fig. 1) using a linear array transducer with a minimum frequency of 7 MHz, attached to a high-quality mainframe ultrasound system.

7. A segment with clear anterior and posterior intimal interfaces between the lumen and vessel wall is selected for continuous 2D grayscale imaging. During image acquisition, anatomic landmarks such as veins and fascial planes are noted to help maintain the same image of the artery throughout the study. A stereotactic probe-holding device can be helpful.

[figure not shown]
[figure not shown]

Figure 1. Ultrasound image of the brachial artery (longitudinally) at 8× magnification, 11-MHz transducer frequency annotated for anatomic landmarks.

